### 7.5.5 To develop response biomarkers for the assessment of ATR and PD-L1 inhibition.

We will attempt to identify signatures of response and resistance by comparing biomarker profiles of tumor biopsies collected on-treatment to baseline profiles, and correlating these with tumor response.

## 7.5.6 To develop and characterize patient-derived xenografts (PDXs) to determine mechanisms of antitumor response and resistance.

Patient-derived xenografts will be established in mice using tumor biopsies obtained from patients at baseline and at time of drug resistance. Molecular profiling will be undertaken with whole exome

sequencing, RNA-seq and RPPA studies to assess mechanisms of antitumor response and resistance. By comparing profiles in PDX tumors from responding and progressing patients, we will attempt to identify signatures of response and progression.

#### 8. ADVERSE EVENT REPORTING

#### 8.1 Adverse Events

All observed or volunteered AEs regardless of treatment group or suspected causal relationship to the investigational product(s) will be reported as described in the following sections.

For all AEs, the investigator must pursue and obtain information adequate both to determine the outcome of the AE and to assess whether it meets the criteria for classification as a serious adverse event (SAE) requiring immediate notification to the Safety Project Manager (MDACC IND Office). For all AEs, sufficient information should be obtained by the investigator to determine the causality of the AE. The investigator is required to assess causality. Follow up by the investigator may be required until the event or its sequelae resolve or stabilize at a level acceptable to the investigator, and the MDACC IND Office concurs with that assessment.

As part of ongoing safety reviews conducted by the MDACC IND Office, any non-serious AE that is determined by the MDACC IND Office to be serious will be reported by the MDACC IRB as an SAE per MDACC institutional policy. To assist in the determination of case severity, further information may be requested from the investigator to provide clarity and understanding of the event in the context of the clinical study.

The active reporting period begins from the time that the patient provides informed consent through 90 calendar days after the last administration of the investigational product(s) unless other anti-cancer therapy is commenced, at which time toxicity follow up will cease at the discretion of the treating physician .

#### 8.2 Definition of Adverse Event

An adverse event is defined in the International Conference on Harmonization (ICH) Guideline for Good Clinical Practice (GCP) as 'any untoward medical occurrence in a patient or clinical investigation subject administered a pharmaceutical product and that does not necessarily have a causal relationship with this treatment,' (ICH E6:1.2).

An adverse event cab therefore be any unfavorable and unintended sign (including an abnormal laboratory finding, for example), symptom or disease temporally associated with the use of a medicinal product, whether or not it is considered related to the medicinal product.

### 8.3 Definition of Serious Adverse Event (SAE)

An adverse event or suspected adverse reaction is considered 'serious' if, in the view of either the investigator or the sponsor, it results in any of the following outcomes:

- a. Death.
- b. A life threatening adverse drug experience any adverse experience that places the patient, in the view of the initial reporter, at immediate risk of death from the adverse experience as it occurred. It does not include an adverse experience that, had it occurred in a more severe form, may have caused death.
- c. Inpatient hospitalization or prolongation of existing hospitalization.
- d. A persistent or significant incapacity or substantial disruption of the ability to conduct normal life functions.
- e. A congenital anomaly/birth defect.

Important medical events that may not result in death, be life threatening, or require hospitalization may be considered a serious adverse drug experience when, based upon appropriate medical judgement, they may jeopardize the patient or subject and may require medical or surgical intervention to prevent one of the outcomes listed in this definition. Examples of such medical events include allergic bronchospasm requiring intensive treatment in an emergency room or at home, blood dyscrasias or convulsions that do not result in inpatient hospitalization, or the development of drug dependency or drug abuse (21 CFR 312.32).

- Important medical events as defined above, may also be considered serious adverse
  events. Any important medical event can and should be reported as an SAE if deemed
  appropriate by the PI or the IND Sponsor (IND Office).
- All events occurring during the conduct of a protocol and meeting the definition of an SAE must be reported to the IRB in accordance with the timeframes and procedures outlined in 'The University of Texas MD Anderson Cancer Center Institutional Review Board Policy for Investigators on Reporting Unanticipated Adverse Events for Drugs and Devices.' Unless stated otherwise in the protocol, all SAEs, expected or unexpected, must be reported to the IND Office, regardless of attribution (within 5 working days of knowledge of the event).
- All life threatening or fatal events, that are unexpected, and related to the study drug(s), must have a written report submitted within 24 hours (next working day) of knowledge of the event to the Safety Project Manager in the IND Office.
- Unless otherwise noted, the electronic SAE application (eSAE) will be utilized for safety reporting to the IND Office and MDACC IRB.
- Serious adverse events will be captured from the time of the first protocol specific intervention, until 90 days after the last dose of drug, unless the participant withdraws consent. Serious adverse events must be followed until clinical recovery is complete and laboratory tests have returned to baseline, progression of the event has stabilized, or there has been acceptable resolution of the event.
- Additionally, any serious adverse events that occur after the 90 day time period, which are
  related to the study treatment must be reported to the IND Office. This may include the
  development of a secondary malignancy.

SAEs in screening will only be captured if they are related to a protocol procedure. Hospitalizations clearly documented as disease progression will not be captured as SAEs unless the patient continues on study.

## 8.4 Reporting to the Federal Drug Administration (FDA)

Serious adverse events will be forwarded to the FDA by the IND Sponsor (Safety Project Manager IND Office) according to 21 CFR 312.32.

It is the responsibility of the PI and the research team to ensure that SAEs are reported according to the Code of Federal Regulations, Good Clinical Practices, the protocol guidelines, the Sponsor's guidelines, and the IRB policy.

#### 8.5 Investigator Communications with EMD Serono

For SAEs, the active reporting period to EMD Serono or its designated representative begins from the time that the patient provides informed consent through 90 calendar days after the last administration of the investigational product. SAEs occurring in a patient after the active reporting period has ended, should be reported to EMD Serono if the investigator becomes aware of them; at a minimum, all SAEs that the investigator believes have at least a reasonable possibility of being related to investigational product(s) are to be reported to EMD Serono.

AEs (serious and non-serious) should be reported on the case report form (CRF) from the time the patient has taken at least one dose of investigational product through the patient's last visit.

[figure not shown]
If a patient begins a new anticancer therapy, the AE reporting period for non-serious AEs ends at the time the new treatment is started. Death must be reported if it occurs during the SAE reporting period after the last dose of investigational product, irrespective of any intervening treatment.

The investigator's primary responsibilities in safety reporting are to identify and follow up on SAEs experienced by participants in the study, and to forward the information to the IRB, IND Office, and EMD Serono, as required by local regulations (for regulatory reporting) and Investigator-Initiated Research (IIR) agreement (for reporting to EMD Serono).

The following reportable events must be submitted to EMD Serono within 24 hours (or immediately for death or life threatening events) using the MDACC SAE form with the EMD Serono Reportable Events Fax Cover Sheet with each SAE submission:

- a. SAEs,
- b. Exposure during pregnancy or breastfeeding (even if not associated with an AE),
- c. Occupational exposure (even if not associated with an AE),
- d. Potential drug-induced liver injury (Hy's Law cases): these events are considered important medical events and should be reported as SAEs.

Contact information for submission of reportable events to EMD Serono:

#### Specifying:

- PROTOCOL NUMBER and/or Title
- EMD Serono assigned Study Number
  - SUBJECT Number
  - SITE Number/PI Name

The MDACC SAE form will be submitted to EMD Serono. The following details must be recorded for each SAE in the SAE report form:

- a. A description of the AE in medical terms according to NCI CTCAE v5.0, not as reported by the subject,
- b. The severity grade as assessed by the investigator according to the definitions in NCI CTCAE v5.0.
- c. The date of becoming serious and the date of becoming known (if different),
- d. The reason for seriousness,
- e. The outcome of the SAE at the time of the report,
- f. Information on administration of the study drug(s),
- g. Information on any treatment procedures necessary for the SAE, concomitant medications, relevant lab tests and relevant medical history.

If in any one subject the same SAE occurs on several occasions, then the SAE in question must be documented and assessed anew each time. The investigator is required to submit SAE Follow up reports until the SAE has resolved or stabilized, and all queries have been answered.

#### 8.6 Recording of Adverse Events

The investigator is responsible for ensuring that all adverse events observed by the investigator or reported by the study participants, are properly recorded in the participant's medical records and the electronic case report form.

The following adverse event attributes must be assigned by the investigator:

- a. Adverse event term according to NCI CTCAE v5.0
- b. Severity grade according to NCI CTCAE v5.0
- c. Start date and stop date (or date of last assessment)
- d. Outcome
- e. Causality to study drug(s) (assessed as either related or unrelated)
- f. Any action taken.

Adverse events will be followed until they resolve to baseline or are considered stable. It will be left to the investigator's clinical judgement to determine whether an AE is related and of sufficient severity to require the subject's removal from treatment or from the study. A subject may also voluntarily withdraw from treatment due to what he or she perceives as an intolerable adverse event. If either of these situations arises, the subject should be strongly encouraged to undergo an end-of-study assessment and be under medical supervision until symptoms resolve or the condition becomes stable.

Pre-existing diseases, when worsening during study therapy, have to be considered as AEs. They can lead to SAEs, if they meet the criteria described in Section 8.3.

Intensity of AEs will be graded using the National Cancer Institute Common Terminology Criteria for Adverse Events (CTCAE), version 5.0. If an adverse event occurs which is not described in the CTCAE version 5.0, the four-point scale below will be used:

- Mild: discomfort noticed but no disruption of normal daily activity.
- Moderate: discomfort sufficient to reduce or affect daily activity.
- Severe: inability to work or perform normal daily activity.

• Life threatening: represent an immediate threat to life.

## 8.6.1 Laboratory Test Abnormalities

Laboratory test results will be recorded on the laboratory results pages of the eCRF. In the event of unexplained abnormal laboratory test values, the tests should be repeated immediately and followed up until they have returned to the normal range and/or an adequate explanation of the abnormality is found.

Laboratory test value abnormalities as such should not be reported on the AE page of the eCRF as adverse events unless they are treatment-emergent and they satisfy one or more of the following conditions for clinical significance:

- a. Accompanied by clinical symptoms.
- b. Lead to a change in study medication (e.g. dose modification, interruption or permanent discontinuation).
- c. Require a change in concomitant therapy (e.g. addition, interruption, discontinuation of, or any other change in a concomitant medication, therapy or treatment).

Please note: any laboratory result abnormality fulfilling the criteria for a serious adverse event should be reported as such, in addition to being recorded as an adverse event in the eCRF.

#### 8.6.2 Pregnancy

Pregnancy per se is not considered an AE. A medical occurrence observed in the mother or fetus/newborn would be considered an AE.

Female patients must be instructed to immediately inform the investigator if they become pregnant during the study. The study treatment must immediately be stopped and the patient withdrawn from the study. Pregnancies occurring up to 6 months after completion of the last treatment cycle must also be reported to the investigator. The investigator must report all pregnancies within 24 hours of knowledge to EMD Serono. The investigator should counsel the patient, discuss the risks of continuing the pregnancy, and the possible effects on the fetus. The patient should be monitored until the conclusion of the pregnancy.

Pregnancy occurring in the partner of a patient participating in the study should also be reported to the investigator, MDACC IND Office, and EMD Serono. The partner should be counseled and followed as described above.

## 8.6.3 Adverse Drug Reactions with Concomitant Medications

The investigators must be aware that for all concomitant medications, the regulations of post-marketing reporting for suspected adverse drug reactions apply, i.e. reporting to the marketing authorization holder or the local regulatory bodies.

#### 9. DATA ANALYSIS/STATISTICAL METHODS

[name]. (Professor, Department of Biostatistics, MDACC) will perform all statistical analyses. Detailed methodology for summary and statistical analyses of the data collected in this trial will be documented as outlined below.

#### 9.1 Analysis Sets

### 9.1.1 Safety Analysis Set

The safety analysis set includes all enrolled patients who receive at least one (1) dose of study medication.

# 9.1.2 DLT Analysis Set

The DLT analysis set is a subset of the safety analysis set and includes all enrolled patients in the dose escalation phase, receive at least one dose of the combination treatment, and either experience DLT during the first cycle (28 days) of treatment, or complete the DLT observation period for the first cycle of treatment.

Patients without DLTs who withdraw from study treatment before receiving at least 75% of the planned dose of each of the investigational products in the combination in Cycle 1 for reasons other than toxicity, which are attributable to the investigational products are not evaluable for DLT. Additional patients will be enrolled in the specific cohort to replace patients who are not considered DLT evaluable.

# 9.1.3 Response Analysis Set

All enrolled patients who receive at least one (1) dose of study medication with baseline assessment and have at least one post-baseline tumor assessment will be considered evaluable for response.

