### **Exploratory Endpoints**

- 1. Correlation between clinical benefit (CBR, ORR, PFS, or OS) and ATM mutations and/or protein loss.
- 2. Assessment of homologous recombination deficiency (HRD) score and replication stress response defect (RSRD) score.
- 3. Immunohistochemistry, immunofluorescence, and flow cytometry analysis of immune cell subsets and markers, including PD-L1.
- 4. Whole exome sequencing, RNA-sequencing, and Reverse Phase Protein Array (RPPA) analysis of pre-, on-treatment, and optional at-progression tumor biopsies.
- 5. PK summary statistics, concentration-time profiles and parameters (e.g. CL, AUC,  $C_{max}$ ,  $T_{max}$ , half-life if estimable).

Study Considerations	
 
Actionable variant(s) in the following DDR genes, based on next generation sequencing (NGS), will be considered in this trial: ARID1A, ATM, ATR, ATRX, BAP1, BARD1, BRCA1/2, BRIP1, CDK12, CHEK2, FANCA, FANCC, FANCD2, FANCE, FANCF, FANCM, MRE11A, MSH2, NBN (NBS1), PALB2, RAD51, RAD51C, RAD51D, SMARCB1, and VHL. Other appropriate aberrations may be considered for patient selection at the discretion of the PI depending on emerging data.
 
CLIA-approved immunohistochemistry analysis of ATM protein loss may also be considered.
 
Interim analysis of toxicity will be performed in cohorts of 10 patients.
 
Interim analysis for futility will be performed in cohorts of 10 patients.
 

Planned Sample	3-6 patients for dose escalation.
Size	30 patients for dose expansion.
	The accrual may be up to 36 patients

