# Dose Expansion for Arm A

- RP2D
- · Patients with advanced solid tumors harboring DDR defects
- N = 10 up to a maximum of 30 patients\*

\*Note: a 3-stage decision with 10 patients at each stage will be used for each regimen in the dose expansion phase of the trial. We will stop after the 1st stage if we see 0 successes in 10 patients,

after the 2nd stage if we see < 2 successes in 20 patients, and we will declare the treatment worthy of further study if we see > 3 successes in 30 patients.

QW = weekly; Q2W = every two weeks; MTD = Maximum Tolerated Dose; RP2D = Recommended Phase 2 Dose

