Dose Level -1	M6620: 120 mg/m  , QW, IV; Avelumab: 800 mg, Q2W, IV

**Note:** other intermediate doses of M6620 may be considered following discussion with EMD Serono.

When avelumab and M6620 are to be administered on the same day, avelumab will be administered first, with an interval of at least 1 hour between infusions.

[figure not shown]

Figure 2: Dose Expansion of the combination of M6620 and avelumab (Arm A)

Interim Analysis for Safety: Patients can have any qualifying DDR aberration for interim safety analysis. We will stop if, at any time during the study, we determine that there is more than an 80% chance that the posterior probability of toxicity (i.e., DLT) is more than 30%.

2Interim Analysis for Futility: Using a 3-stage design with 10 patients in each stage, we will stop after the 1st stage if we see 0 successes in 10 patients, after the 2nd stage if we see <2 successes in 20 patients, and we will declare the treatment worthy of further study if we see >3 successes in 30 patients. If we set p0 (highest success rate for unacceptable treatment) =5% and p1 (lowest success rate for acceptable treatment) =20%, this design has alpha=5%, 80% power and probability of early termination under p0 of 60% after 1st stage and 79% after either 1st or 2nd stage.

Note: This study will not be rejected for efficacy until at least N=10 patients with ATM variants have been evaluated for efficacy.

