#### 9.4 General Statistical Considerations

Tabulations will be produced for appropriate demographic, baseline, efficacy and safety parameters. For categorical variables, summary tabulations of the number and percentage of subjects within each category (with a category for missing data) of the parameter will be presented, as well as two-sided 95% confidence intervals, unless otherwise stated. For continuous variables, the number of subjects, mean, median, standard deviation (SD), minimum,

and maximum values will be presented. Time-to-event data will be summarized using Kaplan-Meier methodology using 25th, 50th (median), and 75th percentiles with associated 2-sided 95% confidence intervals, as well as percentage of censored observations.

No imputation of missing efficacy data is planned. For time-to-event analyses, patients who have no efficacy evaluations for disease recurrence will be considered censored at time 0.

For AEs, missing dates will not be imputed, however, if partial dates are available, they will be used to assess if the AE occurred during the treatment period. Missing severities of AEs will not be imputed and will be considered missing in any tabulations of AE severity. If an AE is missing a response to the question regarding relationship to treatment, the event will be considered to be related.

Evaluations will be performed separately for each trial arm.

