# 9.3 Sample Size Determination

There will be 3-6 patients enrolled per dose level in the dose escalation phase of the combination of M6620 and avelumab.

Each dose expansion arm may have up to 30 patients each. A 3-stage design with 10 patients in each stage will be utilized. We will stop after the 1st stage if we see 0 successes in 10 evaluable patients on RP2D, after the 2nd stage if we see < 2 successes in 20 evaluable patients, and we will declare the treatment worthy of further study if we see > 3 successes in 30 evaluable patients. If we set p0 (highest success rate for unacceptable treatment) = 5% and p1 (lowest success rate for acceptable treatment) = 20%, this design has alpha = 5%, 80% power and probability of early termination under p0 of 60% after 1st stage and 79% after either 1st or 2nd stage.

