# 9.5 Efficacy Analysis

The efficacy population will consist of all patients who receive at least one dose of study medication with baseline assessment and have at least one (1) post-baseline tumor assessment. This population will be used for primary analyses of efficacy.

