# 9.5.1 Efficacy Evaluation

Clinical efficacy will be measured by clinical benefit rate (CBR) per RECIST v1.1 and irRECIST. CBR is defined as complete response (CR) + partial response (PR) + stable disease (SD) > 6 months. Overall response rate (ORR) will be measured using RECIST 1.1 criteria. Secondary efficacy endpoints include objective response (CR+PR), progression free survival (PFS), Duration of Response (DoR), overall survival (OS) and ORR. A 95% CI of response rate will be estimated based on the binomial distribution.

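### Treated patients who die or deteriorate before any scan are dropped from the CBR and ORR denominators, and time-0 censoring can also drop their deaths from PFS and, read literally, OS

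*Combined protocol and SAP*

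**What the plan says.** Section 9.1.3 (Response Analysis Set) requires at least one dose, a baseline assessment, and that patients "have at least one post-baseline tumor assessment will be considered evaluable for response". Section 9.5 defines the efficacy population in the same way and adds: "This population will be used for primary analyses of efficacy". No all-treated efficacy analysis is planned. Section 9.4 rules out imputing missing efficacy data, and no rule counts early death or deterioration as a non-response.

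For time-to-event analyses, section 9.4 (printed twice) says "patients who have no efficacy evaluations for disease recurrence will be considered censored at time 0". It makes no exception for death and does not separate PFS from OS. Section 9.5.1 places OS among the efficacy endpoints: "Secondary efficacy endpoints include objective response (CR+PR), progression free survival (PFS), Duration of Response (DoR), overall survival (OS) and ORR". No section names the analysis set for PFS or OS. The only PFS definition that counts deaths is in Appendix D, for CRPC patients.

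On the decision rule, section 9.3 counts evaluable patients: "We will stop after the 1st stage if we see 0 successes in 10 evaluable patients on RP2D". Section 3.2.1 (Figure 2, note 2) does not: "we will stop after the 1st stage if we see 0 successes in 10 patients". The expansion box in section 3.2 sets "N = 10 up to a maximum of 30 patients", the synopsis says "The accrual may be up to 36 patients", and section 6.5 does not replace patients withdrawn outside the DLT period.

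**The concern.** Being evaluable depends partly on outcome. The first scheduled scan comes at 8 weeks (section 7.3). A treated patient who dies or becomes too ill before any scan cannot have CR, PR or stable disease beyond 6 months. Taking only failures out of the denominator can move CBR and ORR in one direction only, upward.

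For PFS, the death is lost on either reading of the plan. If the section 9.5 population applies, the patient is excluded. If a wider set applies, the patient is in it but censored at time 0. The same two routes reach OS on the literal text. Yet these deaths are known without a scan: section 8.5 requires deaths in the SAE reporting period to be reported, and section 9.6.2 plans a by-patient listing of deaths.

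Efficacy is secondary here, since the primary endpoints are adverse events and DLTs. CBR and ORR are still the activity estimates that readers will take from the trial. The unclear denominator also reaches the futility and go/no-go counts.

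**Working it through.** **The plan's own figures.** The section 9.3 rule stops at 0/10 or at fewer than 2/20, and declares go at 4 or more of 30, with p0 = 5% and p1 = 20%. Exact binomial enumeration gives:

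| Property | Plan | Recomputed |
|---|---|---|
| Alpha | 5% | 4.9% |
| Power | 80% | 80.5% |
| Stop after stage 1 under p0 | 60% | 59.9% |
| Stop by stage 2 under p0 | 79% | 78.7% |

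The design reproduces.

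**Inflation of CBR and ORR.** Let q be the share of treated patients never scanned, all of them failures. The documents give no q; 5% to 30% is an assumed range. With x successes in n treated, the plan reports x/[n(1−q)] instead of x/n, an inflation of 1/(1−q): 1/0.95 = 1.05, 1/0.90 = 1.11, 1/0.80 = 1.25 and 1/0.70 = 1.43.

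Example with 30 treated and 6 successes (exact 95% intervals):

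| Unscanned | Reported | 95% CI |
|---|---|---|
| 0 (all treated) | 6/30 = 20.0% | 7.7–38.6% |
| 2 | 6/28 = 21.4% | 8.3–41.0% |
| 3 | 6/27 = 22.2% | 8.6–42.3% |
| 6 | 6/24 = 25.0% | 9.8–46.7% |

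**Kaplan-Meier.** Write true S(t) = (1−q)·S_scanned(t) + q·S_unscanned(t). Time-0 censoring (or exclusion) reports S_scanned(t). This is largest relative to S(t) when all unscanned patients have died by t, giving at most S(t)/(1−q). A true 60% would appear as up to 0.60/0.95 = 63.2% at q = 5%, or 0.60/0.90 = 66.7% at q = 10%.

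**Go/no-go rule.** This was enumerated patient by patient, with at most 30 treated, no replacement, looks at 10 and 20 evaluable, and go at 4 or more successes. That last condition is an assumption when fewer than 30 are evaluable, because the plan does not cover the case.

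| False-go probability | q = 5% | 10% | 20% | 30% |
|---|---|---|---|---|
| Capped, 5% is an all-treated rate | 5.1% | 5.2% | 5.5% | 5.7% |
| Capped, 5% is an evaluable-patient rate | 4.3% | 3.8% | 2.8% | 1.9% |
| Uncapped, enrol to 30 evaluable (rate 0.05/(1−q)) | 5.7% | 6.7% | 9.4% | 13.4% |
| Mean treated needed if uncapped, 30/(1−q) | 31.6 | 33.3 | 37.5 | 42.9 |

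The first row cannot exceed P(X ≥ 4 | n = 30, p = 0.05) = 6.1%. The uncapped row breaks the 30-patient expansion cap at every q. From q = 10% it also exceeds the 36 − 6 = 30 to 36 − 3 = 33 places left on the synopsis count of 3–6 escalation patients. Section 9.3 gives 3–6 per dose level, which could leave fewer.

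**The case against.** The strongest points on the other side are these.

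- **Small q.** Entry requires ECOG 0–1 and a life expectancy of at least 12 weeks, against a first scan at 8 weeks. The calendar has imaging at end of treatment, section 7.3 asks for an unscheduled scan on suspected progression, and sections 6.2 and 6.4 continue disease evaluation after treatment stops. This stands: the lower end of the range is more plausible, and at q = 5–10% the shift lies well inside the confidence interval. A wide interval does not excuse a bias of known direction that costs little to remove.
- **OS.** The censoring rule speaks of disease recurrence, which OS does not need, so it was probably written for PFS. This also stands: loss of OS events follows from the literal text, and the intent is uncertain. Section 6.4 words survival collection as following progression, so the death-reporting and listing rules in sections 8.5 and 9.6.2 are the better evidence that early deaths are known.
- **Exclusion and time-0 censoring are alternatives.** This is correct. In a set that requires a scan, the censoring rule has essentially nobody to act on. The death is lost by either route, so the conclusion for PFS does not change.
- **Little effect on the decision rule.** Agreed. The wording conflict over who is counted still needs settling.

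**Conclusion.** The concern holds and should be fixed. As written, the plan removes certain failures from CBR and ORR and omits deaths before any scan from PFS; on the literal text it omits them from OS too. The inflation of CBR and ORR is 1/(1−q), or 1.05 to 1.11 at the more plausible q of 5–10% and up to 1.43 at 30%. This rests on an assumed q and on every unscanned patient being a failure. Later Kaplan-Meier values are inflated by at most the same factor. The three-stage rule is little affected under the stated caps, and its false-go probability is not inflated at all if p0 is meant as an evaluable-patient rate. Efficacy is secondary, so the trial's primary conclusions are not at risk; its reported activity estimates are.

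**What to change.** Amend section 9 as follows.

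- **CBR and ORR:** analyse all treated patients, with a patient who has no post-baseline scan counted as a non-success.
- **OS:** analyse all treated patients, with every death an event and others censored at the date last known alive.
- **PFS:** count death before the first scan as an event on the death date. Censor at day 1 only patients alive with no scan.
- **Sensitivity analysis:** keep the scan-evaluable set.
- **Decision rule:** make section 9.3 agree with the synopsis, the expansion box in section 3.2, section 3.2.1 and section 6.5. State which patients the 10/20/30 counts refer to, and whether 5% and 20% are all-treated or evaluable-patient rates.

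The cost is an amendment to an open-label trial with a planned start of January 2020, and less favourable reported rates. No extra patients or data are needed. Clarifying the counts touches the decision rule. If they become all-treated counts and p1 = 20% is an all-treated rate, power stays at 80.5% and alpha at 4.9%. If p1 is an evaluable-patient rate, the success probability per treated patient is 0.20(1−q), and power is 77%, 74%, 65% and 54% at q = 5, 10, 20 and 30%. Counting evaluable patients among 30 treated without replacement already gives only 79%, 76%, 70% and 60%, so the change itself costs about 1 to 6 points.
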